5.3. Strategies for Recruitment and Retention

The site PIs and their staff regularly care for neonates and will recruit eligible subjects from their practice. Each site will clearly and adequately convey that participation is voluntary, and that refusal by the parent or legal guardian of the subject will not impact the care and/or medical treatment provided to the subject.

6. STUDY PROCEDURES AND ASSESSMENTS

6.1 Day 0 – Screening Visit and Informed Consent

6.1.1 Informed Consent

Prior to conducting study activities, written consent will be obtained from the parent(s) or legal guardian(s) of all participating subjects and documented on an informed consent form (ICF) that has been approved by an IRB/Ethics Committee. The ICF must be written in adherence to Good Clinical Practice (GCP) and comply with all elements required by FDA CFR 50.25 and ICH 4.8, state and local regulations, and additional elements relevant to specific study situations, (including a statement that Medline Industries, LP and authorities have access to subject records). A copy of the ICF will be given to the parent(s) or legal guardian(s) of the subject.

6.1.2 Eligibility Screening

Potential subjects will be screened for eligibility by the site PI, via a combination of the screening form provided by Medline Industries, LP, and by a review of the potential subject's medical chart by the site PI and/or their staff.

6.2. Day 1 – Study visit

6.2.1. Collection of arterial blood sample and measurement by CO-oximeter

The arterial blood sample will be collected in the normal course of care and will be measured in the reference CO-oximeter for SaO_2 . The time of the arterial blood sample will be recorded on the CRF by the PI or designee or patient's care team using a calibrated clock as the reference time. No more than three blood draws, resulting in three data pairs per sensor in a subject, will be used for this study. Data pairs may be concurrently collected for each of the two sensors type if sensors can be placed on separate extremities.

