4. STUDY DESIGN

4.1. Overall Design

This study is a multi-site, open-label clinical trial validating the SpO₂ accuracy and precision of Medline's reprocessed pulse oximetry sensors as compared to SaO₂ in arterial blood samples as assessed by CO-oximetry in neonates. The data collection will take place at the sites. The PI or designee will place the Masimo and Nellcor sensors on hands and/or feet of the subject according to the IFU and record the reading. The arterial blood sample used in this study will be taken in the normal course of care and will be measured in the reference CO-oximeter for SaO₂. This arterial sample will be obtained from a systemic artery.

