4.2. End of Study Definition

A subject's participation in the study may end at several critical points:

• When the maximum number of blood draws, as per SOC (three), has been reached

- The maximum duration of sensor wear time has been reached, as per SOC or IFU, whichever occurs first.
- The PI or patient care team believes it is in the subject's best interest to discontinue in the study.
- Parent or legal guardian of the subject withdraws the subject from the study for any reason.

If the subject withdraws from the study, they will be replaced by another subject.

The study will be considered complete upon issuance of a Clinical Study Report that has been approved by the Clinical Affairs Director.

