6.2.2. Data collection using pulse oximeter

At or near the time the first blood sample is collected, the PI or designee will place one or both sensors (Masimo and/or Nellcor sensors) on the subject. If the subject is currently receiving biliruben light therapy, then the biliruben light must be turned off when the pulse oximeter sensor reading is taken. The PI or designee will record the SpO₂ measurement, the subject's heart rate, and the time and location of the measurement on the CRF using a calibrated clock as the reference time.

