6.2.6 Moving and Removing Sensors

The sensors may remain on the subject up-to the same duration as would be used for a SOC pulse oximeter. Thus, the duration the sensors remains on the subject is variable but limited by the SOC for each subject.

Subject specific sensors that are removed in between samplings will be secured by the study team until the next time point use. Sensors may be reused on the same subject but will not be used on another subject. Once a subject has completed participation, their sensor will be collected and returned to Medline Industries, LP.

The study or clinical team may move a sensor from location to location on the subject's body to facilitate care and measurement quality.

If the subject has multiple arterial blood samples collected, 6.2.1-6.2.6 can be repeated up to three times using the same sensor. If a new sensor is used, it shall be noted in the CRF.

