8.2 Randomization

Randomization will not be completed as the data are collected from a convenience sample of subjects.

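### The protocol caps study pairs at three routine draws per infant but neither fixes which draws are used nor records those passed over, so staff could favour stable, high-saturation draws

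*Combined protocol and SAP*

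**What the plan says.** The reference samples are routine-care samples (section 6.2.1): "The arterial blood sample will be collected in the normal course of care and will be measured in the reference CO-oximeter". The same section sets the limit: "No more than three blood draws, resulting in three data pairs per sensor in a subject, will be used for this study".

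The starting point is in section 6.2.2: "At or near the time the first blood sample is collected, the PI or designee will place one or both sensors". Later draws are covered in section 6.2.6: "If the subject has multiple arterial blood samples collected, 6.2.1-6.2.6 can be repeated up to three times using the same sensor". Section 4.2 lists events at which participation may end, among them: "When the maximum number of blood draws, as per SOC (three), has been reached".

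The study is open-label (section 4.1). Sites recruit infants from their own practice (section 5.3), and the PI or designee takes the SpO₂ reading (section 6.2.2). Section 6.2.5 expects that person to judge whether the infant's SpO₂ is stable, although there the judgement concerns sensor location against timing. Section 6.2.3 allows the reading up to 10 minutes either side of the draw.

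Section 8.2 gives the sampling basis: "Randomization will not be completed as the data are collected from a convenience sample of subjects". The exclusion rules in section 8.3 apply to data pairs, that is, to draws already paired. Section 8.4 expects an A_RMS of at most 3% for each sensor.

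**The concern.** A convenience sample of infants limits how far the result generalises. A choice among draws within an infant is a separate step, because it can move the estimate itself. The person pairing the draw can know whether the infant is calm or desaturating. If calmer moments are preferred, the paired draws describe easier conditions than the infant's routine draws as a whole.

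A draw that is never paired leaves no trace in the study data, so no later analysis of the paired data can show whether this happened. A_RMS, the within-subject variance and the limits of agreement in section 8.4 would all be affected.

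**Working it through.** **Inputs.** From section 8.1: 80 pairs per sensor (twice 40), at most three per infant, at least 27 infants. From section 8.4: the 3% target. From the adult accuracy tables in the two instructions for use (Appendix), A_RMS by saturation band:

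| Sensor | 70–100% | 90–100% | 80–90% | 70–80% |
|---|---|---|---|---|
| Neo 2329 | 1.6 | 0.9 | 1.6 | 2.1 |
| MAXN | 1.7 | 1.5 | 1.5 | 2.1 |

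The documents do not give the number of routine draws per infant, the share taken while unstable, or the neonatal error at such draws. These are assumptions wherever used below.

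**Step 1: the plan's own figures.** 2 × 40 = 80, and 80/3 = 26.7, rounded up to 27. Both reproduce. Pooling bands as A_RMS = √(Σ w·A²) with equal thirds gives √((0.81 + 2.56 + 4.41)/3) = 1.61 for Neo and √((2.25 + 2.25 + 4.41)/3) = 1.72 for MAXN, against the stated 1.6 and 1.7. The pooling formula is therefore consistent with the tables.

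**Step 2: shift in saturation, using the documents' errors.** Assume routine draws fall 60/25/15 across 90–100, 80–90 and 70–80%.
- Neo: √(0.60×0.81 + 0.25×2.56 + 0.15×4.41) = √1.7875 = 1.34. All draws at 90–100%: 0.90.
- MAXN: √(0.60×2.25 + 0.25×2.25 + 0.15×4.41) = √2.574 = 1.60. All draws at 90–100%: 1.50.

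With an assumed 80/15/5 mix the starting values are 1.12 and 1.54, so the drops are smaller. Even with every draw in the worst band, A_RMS would be 2.1. On these adult figures no mix reaches 3%.

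**Step 3: what crossing 3% would take.** Let a share u of draws be unstable with error e, and the rest have error s. Then A_RMS = √((1−u)s² + u·e²), and setting this to 3 gives e = √((9 − (1−u)s²)/u).
- s = 1.7, u = 0.30: √((9 − 2.023)/0.30) = 4.8.
- s = 1.7, u = 0.40: √((9 − 1.734)/0.40) = 4.3.
- s = 2.5, u = 0.30: √((9 − 4.375)/0.30) = 3.9.
- s = 2.5, u = 0.40: √((9 − 3.75)/0.40) = 3.6.

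The required unstable error is about 1.7 to 2.3 times the largest adult band value of 2.1.

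**Step 4: how much selection, if errors were that large.** A simulation compared the first three draws with the three calmest of K independent draws, assuming staff always pick correctly:

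| Assumed s, e, u | First three | K = 4 | K = 6 | K = 8 |
|---|---|---|---|---|
| 2.5, 4, 40% | 3.19 | 2.94 | 2.64 | 2.55 |
| 2, 4, 30% | 2.76 | 2.40 | 2.08 | 2.01 |

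With K = 3 there is no difference. Less perfect avoidance gives less: if half of the unstable draws are passed over, the two rows become 2.95 and 2.47.

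**Step 5: does any section fix the draws?** Section 6.1.1 requires consent before study activity, so the first paired draw follows consent, but nothing makes it the first draw after consent. Section 6.2.6 permits repetition without requiring the next draw. Section 4.2 prevents a fourth pair, not the skipping of draws before the third. Section 8.2 speaks of subjects, not of draws within a subject. Section 8.3 cannot reach a draw that was never paired.

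**The case against.** The natural reading of sections 6.2.2, 6.2.6 and 4.2 is first draw, then later draws, up to three. The repetition clause may be permissive only because some infants will have a single gas; section 5.1 asks for one or more. The single Day 1 visit and the limit on sensor wear shorten the period in which a choice could be made. With three or fewer routine draws there is little to choose. This narrows the gap but does not close it, since none of these sections says which draws count.

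The error plot against SaO₂ would show a sample confined to high saturation, and monitors review source data. That is partial protection: it shows what was paired, not how it differs from what was not, and monitors are not asked to compare the two.

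Preferring stable draws is also partly legitimate. The Masimo sensor is indicated for no-motion, well-perfused use, and the Nellcor sensor is contraindicated in low perfusion. With a window of 10 minutes either side, some of the discrepancy in an unstable infant is real change in SaO₂ rather than sensor error. This stands, and it weakens any account of selection as pure downward bias. It does not cover passing over low saturation, because both sensors are specified for 70–100%.

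A reader might infer that A_RMS will be biased, or that a failing sensor would be made to pass. The documents show only that selection is possible, and a reversal at 3% rests wholly on the assumed errors in steps 3 and 4. A reader might also infer that three draws minutes apart could fill an infant's quota with near-duplicates. Draws arise only in routine care, so the study cannot order them, and a consecutive-draw rule without a minimum interval would not prevent this anyway. That argument should not be used.

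**Conclusion.** The gap is real: up to three routine draws are used per infant, their choice is not fixed, and skipped draws are not recorded. It matters only for infants with more routine draws than pairs, or where the starting draw is chosen. The expected direction is a lower A_RMS, supported by the adult bands, but neither the occurrence nor the size of selection can be established from the documents. On the adult errors and an assumed 60/25/15 mix, the most it does is 1.34 to 0.90 (Neo) and 1.60 to 1.50 (MAXN), with no bearing on the 3% target. An effect on that target needs unstable-draw errors of roughly 3.6 to 4.8 under the assumptions in step 3. This is an inexpensive improvement worth making, not evidence that the result will be wrong.

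**What to change.** In sections 6.2.1 and 6.2.6, add: *Pairs are taken at consecutive standard-of-care arterial draws, starting with the first after consent and sensor availability during pre-specified staffed hours, up to three. Any intervening draw in those hours that is not paired is logged with time, reason and, where available from the clinical record, SaO₂.*

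In section 8.4, report the number of unpaired draws, the reasons, and their SaO₂ distribution beside that of the paired draws.

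Each site's staffed hours need to be set in advance, or the discretion returns by another route. SaO₂ for unpaired draws may not come from the reference CO-oximeter, so that comparison is descriptive.

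The cost is slightly less scheduling freedom and a short log. No blood draws are added, and the 80 pairs and 27 infants are unchanged.

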6.2.2. Data collection using pulse oximeter

At or near the time the first blood sample is collected, the PI or designee will place one or both sensors (Masimo and/or Nellcor sensors) on the subject. If the subject is currently receiving biliruben light therapy, then the biliruben light must be turned off when the pulse oximeter sensor reading is taken. The PI or designee will record the SpO₂ measurement, the subject's heart rate, and the time and location of the measurement on the CRF using a calibrated clock as the reference time.

6.2.3 Timing of Data Collection

The ideal time to collect SpO₂ values is <1 minute of the arterial blood sample collection. However, the PI or designee may collect the SpO₂ values up-to 10 minutes before or 10

minutes after the arterial blood sample is collected. It is also ideal to collect both SpO₂ values at the same time. If this is not possible, it is acceptable to collect the SpO₂ values at different times, but still within the ± 10 -minute timeframe of when the arterial blood sample was collected.

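### SpO₂ may be read up to 10 minutes after the draw with no rule that it be recorded before the SaO₂ result is seen, so late readings could be chosen with the reference known, lowering A_RMS by an unknown amount.

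*Combined protocol and SAP*

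**What the plan says.** On timing, section 6.2.3 begins with a preference: "The ideal time to collect SpO₂ values is <1 minute of the arterial blood sample collection". It then relaxes it: "However, the PI or designee may collect the SpO₂ values up-to 10 minutes before or 10" "minutes after the arterial blood sample is collected". The two sensors may also be read at different times within that window.

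On who reads, section 6.2.2 states: "The PI or designee will record the SpO₂ measurement", together with heart rate, time and location against a calibrated clock. Section 6.2.1 allows the same role to log the draw: "The time of the arterial blood sample will be recorded on the CRF by the PI or designee or patient's care team". Of the reference it says only that the sample "will be measured in the reference CO-oximeter for" SaO₂. It names no operator, turnaround time or recipient of the result.

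Section 4.1 describes the study as open-label. Section 8.3 drops a pair if the person collecting the data notes an anomaly on the CRF at collection and before analysis begins. It does not say before SaO₂ is known. Section 8.4 defines A_RMS (equation 1.1) and expects 3% or less for each sensor.

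No section masks the reader, separates the reader from whoever runs or sees the CO-oximeter, logs when the result became known, or fixes which displayed value goes on the CRF.

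**The concern.** The endpoint is agreement between two numbers. One of them is copied by hand from a display that changes over time. If the person copying it already knows the other number, the two are no longer independent, and a site could reach that position while following the plan exactly.

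Three features make late readings plausible. The one-minute timing is a preference only. Under 6.2.2 the sensor need only be placed at or near the time of the first sample. Section 6.2.4 prefers both sensors at the same location, which would tend to make one reading later than the other.

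The anomaly rule in 8.3 has the same weakness: a pair can be flagged after its SaO₂ has been seen. What is at stake is whether an A_RMS at or below 3% reflects the sensor alone.

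**Working it through.** **No plan figure to reproduce.** The point is a missing procedural rule and rests on no stated sample size or power.

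**Direction.** Equation 1.1 is A_RMS = √[Σ(SpO₂ᵢ − SaO₂ᵢ)²/n]. Suppose k values are displayed while the reader watches. An uninformed reader records the first. An informed reader who favours agreement records the one with the smallest |SpO₂ − SaO₂|. That squared difference is never larger than the first value's, so each term, and hence A_RMS, can only fall or stay the same.

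**Size: a model with assumed inputs.** None of these figures is in the documents:
- sensor bias 1.5 points;
- display fluctuation SD s of 0.5, 1.0 or 1.5;
- between-pair SD set so that the true A_RMS stays fixed;
- k = 3;
- informed share f.

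At s = 1.5 the between-pair SD is 2.5, so the true mean square is 1.5² + 2.5² + 1.5² = 2.25 + 6.25 + 2.25 = 10.75, and A_RMS = √10.75 = 3.28%. Holding 10.75 fixed, the between-pair SD is √(10.75 − 2.25 − s²): 2.87 at s = 0.5, 2.74 at s = 1.0 and 2.50 at s = 1.5.

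Simulating 2,000,000 pairs gives the mean square M of the closest of three values: 8.60, 6.66 and 4.95 respectively. With a share f informed, A_RMS = √[f·M + (1 − f)·10.75]:

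| Display SD | f = 5% | f = 25% | f = 50% | f = 100% |
|---|---|---|---|---|
| 0.5 | 3.26 | 3.20 | 3.11 | 2.93 |
| 1.0 | 3.25 | 3.12 | 2.95 | 2.58 |
| 1.5 | 3.23 | 3.05 | 2.80 | 2.22 |

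The two ends of the plausible range, worked through:
- f = 5%, s = 0.5: √(0.05 × 8.60 + 0.95 × 10.75) = √10.64 = 3.26.
- f = 50%, s = 1.5: √(0.50 × 4.95 + 0.50 × 10.75) = √7.85 = 2.80.

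**Share needed to reach 3%.** Setting A_RMS to 3 gives f = (10.75 − 9)/(10.75 − M). That is 1.75/2.15 = 81% at s = 0.5, 1.75/4.09 = 43% at s = 1.0, and 1.75/5.80 = 30% at s = 1.5. Only pairs read after the result is back can be informed, so f cannot exceed the share of such late readings, which is unknown.

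**What the recorded times show.** Draw time and SpO₂ time give the interval between them. That identifies pairs read before, or within a minute of, the draw, where knowledge of the result is unlikely. For later pairs it does not show whether SaO₂ had been seen, because the result time is not recorded.

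**The case against.** A reader might infer that the readings will be biased, or that open-label means the reader sees SaO₂. The documents support neither. Open-label here describes a single convenience sample without randomisation. Bias needs four things together: a result back within 10 minutes, a reading still outstanding, a reader who has seen the result, and a choice made towards it. The plan settles none of these. The stated preference for reading within a minute also steers staff to the protected period. This stands, and it makes the point a risk of bias rather than a demonstrated one.

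A reader might also infer that any such bias would be undetectable. That is too strong. The calibrated-clock times isolate the pairs at risk, and comparing them with pairs read at the draw gives an indirect check, though not proof.

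The assumed true A_RMS of 3.28% is also well above the only empirical figures in the documents, the adult values of 1.6 for Neo 2329 and 1.7 for MAXN in the appended instructions for use. If neonates behave similarly, selection would flatter the estimate without changing its position against 3%. Finally, an uninformed reading taken minutes from the draw adds real drift and tends to raise A_RMS, so the net effect of the wide window could go either way. Both points stand. Neither supplies the missing rule.

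**Conclusion.** The gap is real. The plan permits readings after the draw, leaves the choice of displayed value open, and does not require SpO₂ to be recorded before the reference is known. Selection with the reference known, taken alone, can only lower A_RMS. Whether it occurs depends on turnaround and on who sees the result, which the documents do not give. With the assumed true A_RMS of 3.28% and best-of-three selection, the effect runs from about 0.02 points (5% informed, SD 0.5) to about 0.48 points (50% informed, SD 1.5), so from negligible to crossing 3%. These inputs are illustrative. The change is worth making because the safeguard is nearly free and knowledge of SaO₂ cannot be reconstructed from the data now collected.

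**What to change.** - **6.2.2 and 6.2.3:** require SpO₂, heart rate and time to be written on the CRF before the SaO₂ result is viewed. Fix one value to take: the value displayed at the draw or, if the sensor is not yet reading, the first value displayed once it tracks the pulse.
- **CRF:** add the time the SaO₂ result became available or was viewed.
- **8.3:** require any anomaly flag to be entered before SaO₂ is viewed.
- **8.4:** keep all pairs that pass 8.3 in the primary A_RMS. Add a sensitivity A_RMS limited to pairs read before the draw, within 1 minute of it, or before the recorded result time, and report the number of other pairs.

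Do not instead exclude from the primary analysis pairs that lack a declaration that SaO₂ was unknown. Someone holding the result could then remove a discordant pair by leaving the declaration blank.

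The cost is a few sentences, one CRF field and one extra analysis. Standard-of-care sampling is unaffected.

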6.2.4 Placement of Study Pulse Oximeters

The ideal placement of the sensors is to be on the same location (e.g., same foot, hand, finger, or toe). If this placement is not possible, it is permissible to place the sensors onto different locations.

6.2.5 Conflicting Choice of Same Location versus Same Time

If the preference of measurements at the same time and at the same location cannot both be accommodated, the PI or designeewill be advised to use personal judgement and preferentially pick the solution that will give the most similar measurement (that is selecting the same location (if the patient has a stable SpO₂ over time), or selecting the same time (if the patient has markedly different SpO₂ or perfusion suspected between measurement locations)).

6.2.6 Moving and Removing Sensors

The sensors may remain on the subject up-to the same duration as would be used for a SOC pulse oximeter. Thus, the duration the sensors remains on the subject is variable but limited by the SOC for each subject.

Subject specific sensors that are removed in between samplings will be secured by the study team until the next time point use. Sensors may be reused on the same subject but will not be used on another subject. Once a subject has completed participation, their sensor will be collected and returned to Medline Industries, LP.

The study or clinical team may move a sensor from location to location on the subject's body to facilitate care and measurement quality.

If the subject has multiple arterial blood samples collected, 6.2.1-6.2.6 can be repeated up to three times using the same sensor. If a new sensor is used, it shall be noted in the CRF.

